7. The frequency of liver function and FVIII testing has been increased during the Years 2-5 follow-up period. Testing will be performed every 4 weeks (+ 2 weeks, or as scheduled to align with other scheduled study visits) during year 2, and every 6 weeks (± 2 weeks) during years 3-5.

Rationale: This change will enable more frequent monitoring of subjects' liver function and FVIII testing during the long-term follow-up period and enable investigators to evaluate safety and efficacy more closely.

8. It has been clarified that post-steroid testing for hepatitis B/C reactivation should be performed only in subjects who have a previous history of positive hepatitis B/C tests.

Rationale: The previous language in the protocol was unclear and may have led some investigators to think all subjects (including those with no prior evidence of viral hepatitis exposure) should be retested.

9. The Patient Reported Outcomes, Burdens, and Experiences (PROBE) questionnaire has been added as a quality of life assessment.

Rationale: The PROBE questionnaire will enable assessment of additional patient-reported outcomes of both hemophilia A patients and controls globally.

10. In the event of a positive Bethesda assay result during Years 3-5, an additional sample has been added to be collected within 4 weeks of the visit where the positive result was obtained.

Rationale: During Years 3-5, samples are being regularly collected every 6 weeks. However, to align with EMA guidance (which suggests that a confirmatory test on a second sample should be done within a month after a positive Bethesda assay result), language has been added to require the site to conduct an unscheduled visit within 4 weeks after the date when the positive Bethesda result was obtained.

11. Emicizumab, fitusiran, and concizumab have been added as prohibited medications starting 30 days before Screening and through the end of the study.

Rationale: Experimental hemophilia treatments are prohibited during the study as they could affect the assessment of FVIII levels in 270-301 subjects.

Page 4

12. Subjects will be advised to abstain from blood or sperm donation after BMN 270 infusion until there is no further evidence of vector shedding.

Rationale: Vector shedding in the blood and semen following BMN 270 infusion has been observed, which could serve for vector transmission if subjects were to donate blood or semen following the BMN 270 infusion.

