- ^d Collection for each matrix to occur until at least 3 consecutive negative results are obtained. Collection and testing of semen samples must continue at least through Week 12, even if 3 consecutive negative results in that compartment have already been recorded.
- e Blood samples will be collected to evaluate biochemical, molecular, cellular, and genetic/genomic aspects relevant to hemophilia A, coagulation, and/or AAV gene transfer, and to develop assays used for these evaluations. Subjects may choose to opt out of the exploratory genetic/genomic research being done to study or try to discover genes that are not yet known to be associated with hemophilia A. While exploratory samples will be collected at the time points indicated above, testing of these samples (including those for TGA assay, Direct Thrombin Activity test, and any other exploratory assessments) will be performed only as deemed necessary by the Sponsor.
- ^f Testing for reactivation of hepatitis B and hepatitis C at Week 16 should be performed only in subjects with evidence of prior exposure and who have not received therapeutic oral corticosteroids prior to Week 16; subjects who have received therapeutic oral corticosteroids will have hepatitis B and hepatitis C testing at the time points indicated in Table 9.1.5.

Table 9.1.3: Schedule of Events – Post-Infusion Follow-Up (Week 17-32)

	Follow-Up After BMN 270 Infusion – Weeks*															
Assessment	17	18	19	20	21	22	23	24	25	26	27	28	29	30	31	32
Study Day*	120	127	134	141	148	155	162	169	176	183	190	197	204	211	218	225
Physical examination ^a	X	X	X	X	X	X	X	X	X	X	X	X	X	X	X	X
Weight ^a				X				X				X				X
Assessment of Adverse Events and Concomitant Medications (including review of subject diary for bleeding and FVIII use)	X	X	X	X	X	X	X	X	X	X	X	X	X	X	X	X
Vital Signs	X	X	X	X	X	X	X	X	X	X	X	X	X	X	X	X
Blood chemistry, hematology, and coagulation tests ^b						X				X						X
Urine Tests ^b										X						
Liver Function Tests ^b	X	X	X	X	X	X	X	X	X	X	X	X	X	X	X	X
FVIII assays ^c	X	X	X	X	X	X	X	X	X	X	X	X	X	X	X	X
FVIII antibody titer				X				X		X						X
PCR of vector DNA in blood, saliva, urine, semen, and stools ^d				X				X		X						X
Exploratory biomarker assessments ^e				X				X		X						X

						Follov	w-Up Aft	ter BMN	270 Infu	ısion – W	/eeks*					
Assessment	17	18	19	20	21	22	23	24	25	26	27	28	29	30	31	32
Study Day*	120	127	134	141	148	155	162	169	176	183	190	197	204	211	218	225
Haemo-QOL-A assessment										X						

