9.6 Dietary or Other Protocol Restrictions

There are no dietary or other protocol restrictions for this study. Alcohol should be avoided for the first 52 weeks of the study, and particularly within 48 hours prior to lab work.

Subjects should be advised to abstain from any blood or sperm donation after BMN 270 infusion, until there is no further evidence of vector shedding.

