12.5.1 Once per week (Weeks 1 through 26)

The following procedures will be performed at one visit per week from Weeks 1 through 20:

- Brief physical examination (complete physical examination at Week 26)
- Assessment of Adverse Events and Concomitant Medications (including review of subject diary for bleeding and FVIII use)
- Vital Signs
- Liver Function Tests (refer to Table 9.7.8.3.1)

Page 89

- LFTs may be monitored more or less frequently (and in particular when ALT values are >1.5x ULN) based on discussion between the Medical Monitor and the Investigator and review of subject data, but LFTs will be monitored at least twice weekly during periods when a subject's ALT is ≥ 3x ULN.
- Samples for FVIII Assays
 - o FVIII activity level (chromogenic FVIII assay)
 - o FVIII activity level (one-stage clot FVIII assay)
 - o FVIII coagulation activity exploratory assay
 - o Bethesda assay (with Nijmegen modification) for hFVIII inhibitor level
 - o FVIII protein assay

12.5.2 Week 1 – Day 4

On Day 4 of Week 1, the following procedures will be performed:

- PCR of vector DNA in blood, saliva, urine, semen, and stools
- Liver Function Tests (refer to Table 9.7.8.3.1)

12.5.3 Week 1 – Day 8

On Day 8, the following procedures will be performed, in addition to the weekly assessments required in Section 12.5.1:

• PCR of vector DNA in blood, saliva, urine, semen, and stools

12.5.4 Every 2 Weeks (Week 2, 4, 6, 8, 10, 12, 14, 16, 18, 20, 22, 24, and 26)

At Weeks 2, 4, 6, 8, 10, 12, 14, 16, 18, 20, 22, 24, and 26 the following procedure will be performed:

• PBMC collection

12.5.5 Weeks 2, 4, 10, 16, 22, and 26

At Weeks 2, 4, 10, 16, 22, and 26 the following procedure will be performed:

• Blood chemistry, hematology, and coagulation tests (refer to Table 9.7.8.2.1)

12.5.6 Weeks 2, 3, 4, 6, 8, 12, 16, 20, 24, and 26

At Weeks 2, 3, 4, 6, 8, 12, 16, 20, 24, and 26, the following procedure will be performed:

• PCR of vector DNA in blood, saliva, urine, semen, and stools

Page 90

Collection to occur until at least 3 consecutive negative results are obtained.
 Semen samples should continue to be collected and tested through Week 12,
 even if 3 consecutive negative results in that compartment have been recorded prior to that time point.

12.5.7 Weeks 4, 12, and 26

At Weeks 4, 12, and 26, the following procedure will be performed:

- Haemo-QoL-A assessment
- EQ-5D-5L
- HAL
- WPAI+CIQ:HS
- PROBE

12.5.8 Every 4 Weeks (Weeks 4, 8, 12, 16, 20, and 24) Plus Week 26

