12.6.3 Every 4 Weeks (Weeks 28, 32, 36, 40, 44, 48, 52)

At Weeks 28, 32, 36, 40, 44, 48, and 52, the following procedure will be performed:

• Weight

12.6.4 Weeks 32, 36, 44, and 52

At Weeks 32, 36, 44, and 52, the following procedures will be performed:

- Blood chemistry, hematology, and coagulation tests (refer to Table 9.7.8.2.1)
- FVIII antibody titer

12.6.5 Weeks 32, 36, 40, 44, 48, and 52

At Weeks 32, 36, 40, 44, 48, and 52, the following procedures will be performed:

- Exploratory biomarker assessments
- TGA Assay
- PCR of vector DNA in blood, saliva, urine, semen, and stools
 - Sample testing to occur until at least 3 consecutive negative sample results have been obtained. Subjects who have not had 3 consecutive negative semen samples by Week 52 should continue to have PCR testing of semen every 4 weeks until 3 consecutive negative samples are documented (or upon consultation between the Investigator and Medical Monitor).

12.6.6 Week 32, 36, and 52

At Week 32, 36, and 52, the following procedure will be performed:

- AAV5 TAb Assay
- AAV5 TI Assay

12.6.7 Week 38 and 52

At Weeks 38 and 52, the following procedures will be performed:

Page 93

- Urine Tests (refer to Table 9.7.8.2.1)
- Direct Thrombin test
- VWF:Ag

12.6.8 Week 52

At Week 52, the following procedures will be performed:

- Haemo-QoL-A assessment
- EQ-5D-5L
- HAL
- WPAI+CIQ:HS
- PROBE

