Rationale: ABO blood group results will be collected at Baseline to potentially correlate with FVIII activity level results in an exploratory manner.

8. Clarified that, on the day of infusion, subjects are not required to be admitted to a hospital to receive the infusion (ie, the infusion may be conducted in any facility that has the requisite capabilities to prepare and perform the infusion, as well as monitor subjects for at least 8 hours).

Rationale: Inpatient admission is not required for the infusion and 8-hour post-infusion observation period.

9. Clarified that the requirement for contraception use can end as early as Week 12, in the case that a subject has had 3 consecutive negative semen vector shedding assessments prior to that time point.

Rationale: Language in the protocol that stated that all subjects must continue with contraception for at least 26 weeks after infusion was inconsistent with the statement that semen sampling could be stopped as early as Week 12 if a subject had had 3 consecutive negative assessments. Revised language makes it clear that all subjects must remain on contraception and provide semen samples for assessment through Week 12, but after that timepoint, both contraception and semen sample assessment can be discontinued once 3 consecutive negative results have been obtained.

Page 4

10. Clarified that assessment of concomitant medications and adverse events should be performed at the every 4-week visits during Year 2, and at the every 6-week visits during Years 3-5.

Rationale: Previously, the protocol called for assessment of AEs and concomitant medications every 3 months during Years 2-5; however, assessment at each visit during Years 2-5 is more appropriate and does not significantly increase subject or site burden.

11. Clarified that vector shedding assessments, if required, can be performed at the every 6-week visits during Years 3-5.

Rationale: Previously, the protocol called for vector shedding assessments, if required, to be done every 4 weeks after Week 52 until clearance. During Years 3-5, when subjects are being assessed for FVIII and liver function every 6 weeks, an every 4-week schedule for vector shedding would add to subject burden. Obtaining results every 6 weeks is sufficient to monitor vector shedding for subject safety and also aligns these assessments with the FVIII and liver function assessment visits.

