- 2. Must have been on prophylactic FVIII replacement therapy for at least 12 months prior to study entry. High-quality, well-documented historical data concerning bleeding episodes and FVIII usage over the previous 12 months must be available.
- 3. Treated/exposed to FVIII concentrates or cryoprecipitate for a minimum of 150 exposure days (EDs).
- 4. Willing and able to provide written, signed informed consent after the nature of the study has been explained and prior to any study-related procedures.
- 5. No previous documented history of a detectable FVIII inhibitor, and results from a Bethesda assay or Bethesda assay with Nijmegen modification of less than 0.6 Bethesda Units (BU) (or less than 1.0 BU for laboratories with a historical lower sensitivity cutoff for inhibitor detection of 1.0 BU) on 2 consecutive occasions at least one week apart within the past 12 months (at least one of which should be tested at the central laboratory).

Page 11

NAME OF COMPANY	SUMMARY TABLE	FOR NATIONAL
BioMarin Pharmaceutical Inc.	Referring to Part of the	AUTHORITY USE
[name]	Dossier:	ONLY:
[name]		
	Volume:	
NAME OF FINISHED PRODUCT:		
BMN 270	Page:	
NAME OF ACTIVE DIGDEDIENT		
NAME OF ACTIVE INGREDIENT:	Reference:	
AAV5-hFVIII-SQ		

- 6. Sexually active participants must agree to use an acceptable method of effective contraception, either double-barrier contraception (ie, condom + diaphragm; or condom or diaphragm + spermicidal gel or foam) or their female partner either using hormonal contraceptives or having an intrauterine device. Participants must agree to contraception use for at least 12 weeks post-infusion; after 12 weeks, subjects may stop contraception use only if they have had 3 consecutive semen samples with no detectable viral vector DNA.
- 7. Willing to abstain from alcohol consumption for at least the first 52 weeks following BMN 270 infusion.
- 8. HIV positive patients may be enrolled, only if the patient has a CD4 count > 200/mm³ and an undetectable viral load (unquantifiable viral load as defined as less than the limit of quantification by the testing laboratory's assay is permitted)

Patients are excluded from the study if any of the following criteria apply:

- 1. Detectable pre-existing antibodies to the AAV5 capsid.
- 2. Any evidence of active infection or any immunosuppressive disorder, except for HIV infection as described in the inclusion criterion above.

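### Amendment 2 inclusion criterion 6 lets any earlier run of three vector-negative semen samples end contraception after 12 weeks, even when a later mandatory sample is positive

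*Protocol*

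**What the plan says.** **Contraception.** Criterion 6 in the Amendment 2 synopsis requires contraception for at least 12 weeks after infusion, and then: "after 12 weeks, subjects may stop contraception use only if they have had 3 consecutive semen samples with no detectable viral vector DNA". Amendment 1, Section 9.3.1, has the same three-sample condition with a six-month minimum.

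**How the sponsor reads it.** Item 9 of the Amendment 2 summary of changes says the requirement can end as early as Week 12 where "a subject has had 3 consecutive negative semen vector shedding assessments prior to that time point". Its rationale adds that, after Week 12, "both contraception and semen sample assessment can be discontinued once 3 consecutive negative results have been obtained".

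**Sampling (Amendment 1).** Footnote d of Table 9.1.2 sets a floor: "semen samples must continue at least through Week 12, even if 3 consecutive negative results in that compartment have already been recorded". Section 12.5.6 repeats this: "even if 3 consecutive negative results in that compartment have been recorded prior to that time point". For later Year 1 visits, Section 12.6.5 has "Sample testing to occur until at least 3 consecutive negative sample results". Table 9.1.4 footnote d and Section 12.7.4 drop testing in Years 2 to 5 once three consecutive samples in Year 1 have been clear. The continuation of semen testing past Week 52 applies only to men who have not yet had such a run.

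**What pulls the other way.** Amendment 1, Section 9.7.8.6, allows that contraception might have to run past 26 weeks in some men because of shedding seen in semen. The next sentence returns to the same three-negatives condition. On donation, Section 9.6 advises subjects to "abstain from any blood or sperm donation after BMN 270 infusion, until there is no further evidence of vector shedding".

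**The concern.** The condition is historical: it asks whether three consecutive negatives have ever occurred, not whether the man is negative now. That would be harmless if sampling ended with the run, but semen must still be collected and tested through Week 12. The protocol therefore gathers results after a qualifying run and, in the text shown, attaches no consequence to a positive among them.

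At stake is a partner-protection measure. Followed literally, the rule allows a man whose latest semen result is positive to stop contraception. If the Amendment 1 sampling wording survives in the current version, it also allows the sampling that would show when he clears to stop.

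**Working it through.** The plan states no figure on this point, so there is none to reproduce. The check is a count on the schedule, followed by one worked case.

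**Inputs.** Vector DNA PCR rows of Amendment 1, Tables 9.1.2 to 9.1.4, with study days from the same tables.
- Follow-up samples through Week 12: Day 4, Day 8, Weeks 2, 3, 4, 6, 8 and 12, so 8 samples.
- Later Year 1 samples: Week 16 (1); Weeks 20, 24, 26 and 32 (4); Weeks 36, 40, 44, 48 and 52 (5). 1 + 4 + 5 = 10.
- Week 12 is Day 85 and Week 24 is Day 169.

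**Runs that can qualify by Week 12.** The number of runs of 3 in 8 samples is 8 − 3 + 1 = 6, ending at Weeks 2, 3, 4, 6, 8 and 12. Five of the six are complete before the Week 12 sample. After those five, 5, 4, 3, 2 or 1 mandatory samples remain, and as worded none of them can undo the run. This leaves out the infusion-day sample, taken 2 to 24 hours after infusion (Table 9.1.1 footnote k). Counting it, a run could be complete by Day 8.

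**Worked case: negative at Weeks 4, 6 and 8, positive at Week 12.**

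| Provision | Condition met? |
|---|---|
| Amendment 2 criterion 6, contraception after 12 weeks | Yes |
| Amendment 1 Section 9.3.1, contraception after 6 months | Yes |
| Amendment 1 Table 9.1.2 footnote d, Sections 12.5.6 and 12.6.5, semen sampling after Week 12 | Condition for ending already met; none of the 10 later Year 1 samples is required |
| Amendment 1 Table 9.1.4 footnote d, Section 12.7.4, Years 2 to 5 | Testing not required |
| Amendment 1 continuation of semen testing past Week 52 | Does not reach him, since he has had a run |
| Amendment 1 Section 9.6, sperm donation | Must still abstain |

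The first row is the point. The other contraception and sampling rows rest on Amendment 1 text.

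**Under a most-recent rule.** After a positive Week 12 sample, the earliest three most recent negatives are Weeks 16, 20 and 24. That is 3 samples already scheduled and 169 − 85 = 84 days. A man negative at Weeks 6, 8 and 12 qualifies at Week 12 under either rule.

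**Reach of the wording.** With the infusion-day sample there are 9 results and 2^9 = 512 possible negative/positive patterns. Of these, 238 contain some run of three negatives and 2^6 = 64 end in one. The remaining 238 − 64 = 174 qualify as worded although a positive follows the run. These are counts of patterns, not probabilities.

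**The case against.** **The text may be superseded.** The note to file names protocol version 7.0 (15 July 2021). What is shown stops within the Amendment 2 synopsis of June 2018, and Amendment 2 says it revised the contraception and semen-sampling language. This stands for the sampling and Years 2 to 5 provisions: they are quoted from Amendment 1, and for Amendment 2 only a summary of changes supports them. It does not remove the criterion 6 point, which is Amendment 2's own wording. The schedule counts do combine Amendment 2's 12-week minimum with Amendment 1's visits.

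**The condition is necessary, not sufficient.** Literally, criterion 6 says who may not stop, and as an eligibility criterion it is not the operating procedure. Sampling until at least three negatives is also a minimum. This is fair as grammar, but the Amendment 2 summary treats the condition as permission to stop and counts runs completed before Week 12. The summary is used here only to confirm how the criterion is meant to work.

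**A clinician would act on a positive Week 12 sample.** Probably so, and Section 9.7.8.6 of Amendment 1 leaves room for it. That sentence is discretionary, concerns use beyond 26 weeks, and does not restore sampling. It softens the practical risk without correcting the criterion.

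**A stronger reading that does not hold.** A reader might take item 12 of the Amendment 1 summary ("Vector shedding in the blood and semen following BMN 270 infusion has been observed, which could serve for vector transmission") as the protocol's own statement that partners are at risk. The sentence goes on to make this conditional on subjects donating blood or semen. It is the rationale for the donation advice and does not address partners or contraception.

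**Conclusion.** The point holds for Amendment 2 criterion 6. As worded, and as the Amendment 2 summary reads it, a run of three negatives completed before Week 12 satisfies the condition for stopping contraception even if a later mandatory sample is positive. The donation rule in Section 9.6 of Amendment 1 shows that the protocol already uses a current-status standard for the same fluid.

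Two further inferences should not be drawn. The shown text does not establish that the operative protocol stops semen sampling after a positive. It shows that Amendment 1's sampling wording has the same any-run form, to be checked against the current version. Nor does the text direct anyone to stop: these are permissions.

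Severity is minor. The document gives no data on how often a positive follows three negatives, and no frequency or harm rate is claimed. The counts of 6 runs, 5 complete early, 10 later samples and 84 days assume the Amendment 1 visit schedule.

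**What to change.** In criterion 6, require that the three most recent consecutive post-infusion semen samples, the last taken at Week 12 or later, be negative, and that any positive restart the count. Make the same change in the shedding text (Tables 9.1.2 to 9.1.4 footnote d; Sections 9.7.8.6, 12.5.6, 12.6.5 and 12.7.4) wherever the current version keeps the any-run wording. No change is needed where it already says this. The length of the minimum contraception period remains the sponsor's choice.

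The cost is one phrase in each place and no added Year 1 visit. Men with intermittent positives would continue contraception and already scheduled sampling for longer; the 3 samples and 84 days after a positive Week 12 sample are a minimum.
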